5.1 Inclusion Criteria

Inclusion criteria that must met prior to the first vaccination:

- 1. Comprehension of informed consent.
- 2. 18-45 year old men or women with acknowledged active IDU in the past 90 days and have no travel plans that would interfere with ability to meet the study visit schedule.
- 3. In good general health as determined by a participating study physician and results within acceptable ranges for clinical laboratory evaluations as detailed in Appendix A.
- 4. Negative for antibodies to hepatitis C virus (anti-HCV).
- 5. Negative for HCV RNA.
- 6. Negative antibodies to HIV.
- 7. Negative for HBsAg.
- 8. Able and willing (in the Investigator's opinion) to comply with all study requirements.
- 9. Willing to allow the investigators access to their medical records.
- 10. Willingness to practice continuous effective contraception from the screening visit through 90 days after the last vaccination (males and females).
- 11. Among females, a negative pregnancy test within 24 hours prior to vaccination.
- 12. Agreement to refrain from blood donation during the course of the study or after the study.
- 13. Provide written informed consent prior to initiation of any study procedures.
- 14. Willing to provide contact information for study follow-up activities, including the address, name and contact information of three people who can be contacted to facilitate follow-up compliance.

5.2 Exclusion Criteria

Exclusion criteria that apply prior to the first vaccination:

- 1. The subject is currently participating in a study that involves an experimental agent (vaccine, drug, biologic device, blood product, or medication) or has received an experimental agent within 30 days prior to enrollment in this study, or expects to receive another experimental agent during participation in this study.
- 2. Prior receipt of a recombinant simian or human adenoviral vaccine or MVA vaccine.
- 3. Administration of immunoglobulins and/or any blood products within the 90 days preceding the planned administration of the vaccine candidate.
- 4. Any confirmed or suspected immunosuppressive or immunodeficient state, including: HIV infection; asplenia; recurrent, severe infections.
- 5. History of allergic disease or reactions likely to be exacerbated by any component of the vaccine (i.e., known hypersensitivity to aminoglycoside antibiotics or to egg proteins).
- 6. History of clinically significant contact dermatitis or other significant dermatological conditions such as psoriasis.
- 7. Any history of anaphylaxis in reaction to vaccination.
- 8. Pregnancy, lactation or willingness/intention to become pregnant during the study.
- 9. History of cancer (except for successfully treated basal cell carcinoma of the skin and cervical carcinoma in situ).
- 10. History of severe psychiatric illness, including severe depression, history of suicidal ideation, suicidal attempts, or psychosis requiring medication. The subject has a diagnosis of schizophrenia, bi-polar disease, or other severe (disabling) chronic psychiatric diagnosis that is uncontrolled and would interfere with the ability to adhere to the protocol.
- 11. Any other serious chronic illness requiring hospital specialist supervision.
- 12. Suspected or known current alcohol abuse as defined by a score of 10 or more on the Alcohol Use Disorders Identification Test (AUDIT) C test (a standardized screening tool used to identify hazardous drinkers or those with active alcohol use disorders, including abuse or dependence).⁸²
- 13. At high risk of HIV infection by the following criteria (adapted from HIV Network for Prevention Trials (HIVNET) behavioral criteria for high risk of HIV): (1) sexually active male who has sex with men (MSM), defined as (i) male who has had anal sex with male sexual partner or partners in the past year or (ii) a male

who exchanged sex with male partner(s) for money or drugs in the past year; and (2) female and in a current relationship with a high risk male (active MSM, HIV positive male).⁸³

- 14. Any other significant disease, disorder or finding, which, in the opinion of the Investigator, may put the subject at risk because of participation in the study, may influence the result of the study, or may influence the subject's ability to participate in the study.
- 15. History of or current diagnosis of Diabetes mellitus.
- 16. History of or current diagnosis of autoimmune disease.
- 17. History of or current cardiac disease including history of myocardial infarction or arrhythmia.
- 18. Current diagnosis of active liver disease.
- 19. History of seizure disorder or currently taking anti-convulsant therapy that would interfere with safety evaluation.
- 20. Uncontrolled hypertension (defined as systolic blood pressure being greater than 140mm Hg or diastolic blood pressure being greater than 90mm Hg).
- 21. History of splenectomy.
- 22. Long term immunosuppressive use (defined as taken for 14 days or more in total at any time during the past 180 days) of high dose oral or parenteral glucocorticoids (high dose defined as prednisone ≥ 20 mg total daily dose, or equivalent dose of other glucocorticoids); or high-dose inhaled steroids (high dose defined as >800 mcg/day of beclomethasone dipropionate or equivalent); or any use of hepatotoxic or non-FDA approved medication.
- 23. Have an acute illness, including an oral temperature greater than or equal to 100.4°F, within 7 days prior to the first vaccination.
- 24. Immunization against another pathogen within 14 days of planned injection.

Second vaccination exclusion criteria:

The following events associated with vaccine immunization constitute absolute contraindications to further administration of vaccine. The subject will not receive additional vaccination, but will continue with scheduled follow-up procedures except vaccination.

- 1. Anaphylactic reaction following administration of vaccine.
- 2. Pregnancy. If a woman reports having a positive home urine pregnancy test or a positive in clinic urine pregnancy test prior to a scheduled second vaccination, she is not eligible to receive the study vaccine. If she later returns to clinic and reports

having a negative home urine pregnancy test and this is confirmed by a negative in clinic urine pregnancy test and a negative blood pregnancy test she may be eligible for the second vaccination if she is still within the vaccination window and no other exclusion criteria are met.

The following adverse events constitute contraindications to administration of vaccine at that point in time. If any one of these adverse events occurs at the time scheduled for vaccination, the subject may be vaccinated at a later date (within 28 days of scheduled administration) or withdrawn at the discretion of the investigator. The subject will not receive additional vaccination, but will continue with all scheduled follow-up procedures except vaccination.

- Acute disease at the time of vaccination (acute disease is defined as the presence of a moderate or severe illness with or without fever). The vaccine dose can be administered to persons with a minor illness such as diarrhea, mild upper respiratory infection with or without low-grade febrile illness, i.e., temperature of <38°C (100.4°F).
- 4. Temperature of >38°C (100.4°F) at the time of vaccination.
- 5. Immunization against another pathogen within 14 days of vaccination.

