5.4 Withdrawal

5.4.1 Reasons for Withdrawal

Subjects may withdraw or be withdrawn for any of the reasons given below. The reason for withdrawal will be recorded in the data collection form. The DSMB may recommend withdrawal of subjects.

In accordance with the current revision of the Declaration of Helsinki (amended October 2000, with additional footnotes added 2002 and 2004) and any other applicable regulations, a subject has the right to withdraw from the study at any time and for any reason and is not obliged to give his or her reasons for doing so. The Investigator may withdraw the subject at any time in the interests of the subject's health and well-being. In addition the subject may withdraw/be withdrawn for any of the following reasons:

- Administrative decision by the Investigator.
- Ineligibility (either arising during the study or retrospective, having been overlooked at screening).
- Significant protocol deviation.
- Subject non-compliance with treatment regime or study requirements.
- An adverse event which requires discontinuation of the vaccination regimen or results in inability to continue to comply with study procedures (see below).

If a subject is withdrawn from the study, all study procedures (except for another vaccination) including safety follow-up will be continued, if possible. If voluntary withdrawal occurs, the subject will be asked to continue scheduled study procedures (except for another vaccination) including safety evaluations, if possible, and be given

appropriate care under medical supervision if symptoms of any AE related to participation in the study are continuing. The subject will be followed until the AE is resolved or until the subject's condition becomes stable. (Note: These plans regarding follow-up only apply if the subject received at least one study dose.)

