- Study personnel will review and record all AE/SAEs and concomitant medications on the appropriate data collection form.
- Approximately 23 mL of venous blood will be collected for hematology and biochemistry parameters, as described in Section 7.6.1, and performed by the local laboratory.
- Approximately 10 mL of venous blood will be collected for HCV viremia.
- Approximately 160 mL of venous blood will be collected for immunologic assays.
- Counseling on avoidance of HCV and HIV infection, and pregnancy will be conducted.
- Referral to drug treatment and needle exchange programs will be provided.

8.2.5 Day 56, Visit 6, Dose 2

(Window: Day 49 to 63)

- Eligibility criteria for receipt of Dose 2 will be reviewed with the subject see Section 5.1 and 5.2.
- Current health status will be reviewed and any changes since the last visit will be recorded.
- The vaccination site will be examined.

- Vital signs will be obtained, including oral temperature, pulse, and blood pressure.
- All concomitant medications will be reviewed for accuracy and completeness. Any new medications will be recorded and assessed for continuing eligibility.
- A targeted physical examination may be performed, as indicated, based on subject's recent clinical history since the screening visit.
- A urine or serum pregnancy test must be performed within 24 hours prior to vaccination for all female subjects of childbearing potential. Results must be negative and known prior to vaccination. If the screening visit is Day -1, a negative pregnancy test obtained at Day -1 may be used for eligibility at Day 0. If the pregnancy test is > 24 hours prior to vaccination, it must be repeated to determine eligibility.
- Approximately 23 mL of venous blood will be collected prior to vaccination for hematology, coagulation and chemistry/metabolic biochemistry parameters, as described in Section 7.6.1, and performed by the local laboratory.
- Approximately 10 mL of venous blood will be collected prior to vaccination for HCV viremia.
- Approximately 100 mL of venous blood will be collected prior to vaccination for baseline immunology assessments.

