11.4 Final Analysis Plan

11.4.1 Definition of Analysis Cohorts

The safety analysis cohort will consist of all randomized subjects who receive at least one vaccination.

The mITT efficacy analysis cohort will consist of all randomized subjects who receive at least one vaccination, are not HCV infected at the first vaccination, and have sufficient follow-up to be evaluable for efficacy. For the primary efficacy endpoint of chronic HCV infection, sufficient follow-up will consist of at least three clinic visits following the second vaccination. If the second dose of vaccine was not administered, the target date for the second dose will be used in this calculation. Subjects who receive treatment for acute HCV infection will be censored from time to event analyses of chronic infection at the date of first treatment.

The according to protocol (ATP) efficacy analysis cohort is a subset of the mITT analysis cohort, excluding subjects with major protocol deviations that would compromise the assessment of vaccine efficacy. Subjects who meet any of the criteria listed below will be censored from time to event analyses according to the date of first occurrence of the criteria, and will be excluded from all other types of analyses. The ATP cohort will exclude subjects who: a) receive treatment for acute HCV infection; b) were enrolled but subsequently found to have been ineligible at enrollment based on a criterion that could reasonably be expected to affect vaccine efficacy; c) did not receive both doses of vaccine or control; d) acquired HCV infection prior to receipt of the second vaccination; e) received the wrong (non-randomized) product at either dose; f) received the second dose fewer than 42 days or more than 70 days after the first dose; g) received an immunosuppressant other than inhaled or topical steroids; h) were immunized against another pathogen or received immunoglobulins or other blood products within 14 days of either dose of study vaccine; i) have autoimmune disease: and i) have a confirmed or suspected immunosuppressive or immunodeficient state. Membership in the ATP efficacy cohort will be assessed by a centralized clinical review prior to unblinding of the study data.

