6.3.3. According to Protocol Population

The according to protocol (ATP) population is a subset of the mITT analysis cohort, excluding subjects with major protocol deviations that would compromise the assessment of vaccine efficacy (see list below). Subjects who meet any of the criteria listed below will be censored in time to event analyses according to the date of first occurrence of the criteria, and will be excluded from all other types of analyses. The ATP cohort will exclude subjects who:

- a. receive treatment for acute HCV infection;
- b. were enrolled but subsequently found to have been ineligible at enrollment based on a criterion that could reasonably be expected to affect vaccine efficacy (as reviewed by the blinded clinical review team [see below]);
- c. did not receive both doses of vaccine or control;
- d. acquired HCV infection prior to receipt of the second vaccination;
- e. received the wrong (non-randomized) product at either dose;
- f. received the second dose fewer than 42 days or more than 70 days after the first dose;
- g. received an immunosuppressant other than inhaled or topical steroids;
- h. were immunized against another pathogen or received immunoglobulins or other blood products within 14 days of either dose of study vaccine;
- i. have autoimmune disease; and
- j. have a confirmed or suspected immunosuppressive or immunodeficient state.

Membership in the ATP efficacy cohort will be assessed by a centralized, blinded, clinical review team comprised of the site PIs and the sponsor prior to unblinding of the study data.

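### For a temporary contraindication at the second dose, Protocol 5.2 and SAP 4.3.2 allow a deferred dose and then, read literally, rule it out; the deferral limit also outruns the Visit 6 window and the ATP interval

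*Protocol*

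**What the plan says.** Protocol 5.2 sets out two groups of events that bear on the second vaccination.

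- **Absolute contraindications** (anaphylaxis, pregnancy). The rule is "The subject will not receive additional vaccination, but will continue with scheduled follow-up procedures except vaccination". The pregnancy item carries its own exception: a woman whose later tests are negative may still be dosed if she is within the vaccination window.
- **Temporary contraindications** (moderate or severe acute illness, fever, a recent immunization against another pathogen). They are introduced with "The following adverse events constitute contraindications to administration of vaccine at that point in time". For these, "the subject may be vaccinated at a later date (within 28 days of scheduled administration) or withdrawn at the discretion of the investigator". The sentence that follows is "The subject will not receive additional vaccination, but will continue with all scheduled follow-up procedures except vaccination".

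SAP 4.3.2 carries both sentences of the temporary paragraph unchanged.

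Four other provisions bear on the point:

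- Protocol 5.4.1, on withdrawal: "If a subject is withdrawn from the study, all study procedures (except for another vaccination) including safety follow-up will be continued, if possible".
- Protocol 8.2.5 (Visit 6, Dose 2): "Window: Day 49 to 63". Staff are told there to check eligibility for Dose 2 against Sections 5.1 and 5.2.
- ATP criterion c (SAP 6.3.3, also in Protocol 11.4.1) excludes subjects who "did not receive both doses of vaccine or control".
- ATP criterion f (Protocol 11.4.1, also in SAP 6.3.3) excludes subjects who "received the second dose fewer than 42 days or more than 70 days after the first dose".

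**The concern.** The two sentences on temporary contraindications are adjacent and have the same grammatical subject. One permits a later dose and the other denies any further dose. Both cannot apply to the same person. Section 5.2 is the text that staff are sent to at Visit 6, so the conflict arises when the dosing decision is made, and three sites have to resolve it for themselves.

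The choice has two consequences. It determines whether a subject receives the boost (or second placebo). It also determines whether that subject can be in the ATP cohort, which carries the primary efficacy analysis and the 43-event target. A subject without Dose 2 can still be in the mITT cohort, where the target date stands in for the missing dose when follow-up is counted (Protocol 11.4.1, SAP 3.3.7).

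**Working it through.** **1. The two readings side by side.**

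- *Reading A:* the bar covers only subjects whom the investigator withdraws, and the others may be dosed late. This fits Protocol 5.4.1, which also has withdrawn subjects continue everything except vaccination. But the sentence in 5.2 refers simply to the subject, and 5.4.1 concerns withdrawal from the study, whereas 5.2 does not say what the subject is withdrawn from.
- *Reading B:* the bar covers every subject with a temporary contraindication. This is the literal sense of the sentence, but it leaves the deferral clause with nothing to do.

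Neither document contains words that choose between them.

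**2. How far the deferral runs.** Dose 1 is at Day 0 and Dose 2 is scheduled for Day 56.

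- Latest deferred dose: 56 + 28 = Day 84.
- Past the end of the Visit 6 window: 84 − 63 = 21 days.
- Past the ATP limit of 70 days: 84 − 70 = 14 days.
- If the scheduled date is taken as either end of the Visit 6 window, the limit is 49 + 28 = Day 77 or 63 + 28 = Day 91. Both exceed 70.

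Of the 28 days allowed after Day 56, the first 14 (to Day 70) are compatible with criterion f and the last 14 (Days 71 to 84) are not.

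**3. Consequence for a subject deferred from Day 56 and otherwise ATP-eligible.**

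| Handling | Dose 2 | ATP status |
|---|---|---|
| Reading A, dosed by Day 70 | given | stays in |
| Reading A, dosed Day 71 to 84 | given | out, criterion f |
| Reading A, withdrawn | not given | out, criterion c |
| Reading B | not given | out, criterion c |

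The reading changes ATP status only for subjects who could be dosed by Day 70. It changes receipt of Dose 2 for everyone who could be dosed by Day 84.

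**4. Effect on power.** Inputs from Protocol 11.2 and SAP 5: hazard ratio 0.40 (60% reduction), two-sided alpha 0.05, power 85%, 43 ATP events.

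The plan's figure, by the Schoenfeld formula with 1:1 allocation:

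d = 4(1.960 + 1.036)² / (ln 0.40)² = 35.91 / 0.8396 = 42.8, so 43 events. The plan's number reproduces.

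Power for d events = Φ(0.9163 × √d / 2 − 1.960):

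- d = 43: Φ(3.004 − 1.960) = 85.2%
- 5% of events lost, d = 40.85: Φ(2.928 − 1.960) = 83.4%
- 10% of events lost, d = 38.70: Φ(2.850 − 1.960) = 81.3%

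The 5% and 10% are assumptions, since the documents give no frequency of temporary contraindications. They act as upper bounds for those frequencies, because they suppose that every affected subject is otherwise ATP-eligible, could have been dosed by Day 70, and is at a site that applies Reading B.

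**The case against.** The strongest reply is that context already settles the meaning. The disputed sentence comes straight after the option to withdraw the subject, and describes what would happen to a withdrawn subject. Protocol 5.4.1 gives the same rule for withdrawals, and SAP 4.3.2 places that withdrawal text directly after the list of temporary contraindications. Reading B would empty the deferral clause and merge the temporary group with the absolute one. Other text also expects a movable second dose: the ATP interval runs to 70 days although the visit window closes at Day 63, Visits 7 and 8 are timed from actual receipt of Dose 2, and SAP Table 7 lists delayed and missed administration separately.

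This makes Reading A plausible, and a reader should not infer that the plan bars a deferred dose outright. Nor does the near-identical sentence under the absolute contraindications prove such a bar, because there it coexists with a permitted later dose once pregnancy is ruled out. That exception, however, is written out in the pregnancy item, and the temporary paragraph has no comparable words limiting its closing sentence. A site still has to supply the limit by inference. The reply also leaves the mismatch between 28 days, Day 63 and 70 days untouched.

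On size, the reply is right that the effect is modest. The plan's 65% retention assumption already allows for ATP losses from any cause, which would include missed second doses, and doses on Days 71 to 84 leave ATP whichever reading is used. Assessments are made by blinded staff (Protocol 6.1.4), and SAP 4.4.2 says that randomization is stratified by site, so differences in site practice should fall similarly on both arms.

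**Conclusion.** The concern holds as an internal inconsistency in operative text, present in both documents. As written, the plan does not say whether a subject with a temporary contraindication may receive a deferred second dose or, if so, how that allowance fits the visit window and the ATP interval. What is directly at stake is receipt of Dose 2 and membership of the primary cohort.

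The number of subjects affected cannot be derived from the documents. Under the assumed losses, power drops by about 2 points (5% of events) or 4 points (10% of events) from about 85%. A reader might go further and infer a definite loss of ATP subjects or a biased vaccine effect. The documents support neither: the first needs a frequency that they do not give and must allow for criterion f, and nothing in them makes deferral differ by arm. They also contain no evidence that sites have acted differently.

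**What to change.** - In Protocol 5.2 and SAP 4.3.2, state which subjects the sentence on no additional vaccination covers: all subjects with a temporary contraindication, or only those whom the investigator withdraws. If the latter, say what they are withdrawn from.
- Reconcile the 28-day deferral limit with the Visit 6 window in Protocol 8.2.5 and with ATP criterion f in Protocol 11.4.1 and SAP 6.3.3. If the limits are meant to differ, say so, and state the ATP consequence of a dose given within the deferral limit but after Day 70.
- Use identical wording in both documents and at all three sites.

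Which clinical rule applies, and which limit, is for the sponsor to decide. The cost is a clarified sentence or two in the protocol, the same text in the SAP, and a memo to sites. No new data collection or change in sample size is needed.
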